2.1.2. SECONDARY SAFETY ENDPOINT

The second safety endpoint will be the number and proportion of participants per dose group and randomized allocation, with:

- at least one episode of cough or spasmodic cough, described by grade, between Day 4 and Day 28
- at least one solicited or unsolicited AEFI from respiratory tract between Day 0 and Day 28
- at least one AEFI with difficulties in breathing (asthma, spasmodic cough, pneumonia) between Day 0 and Day 28
- at least one other AEFI from the respiratory tract between Day 0 and Day 28
- at least one episode of cough, described by grade, between Day 0 and Day 28
- at least one episode of spasmodic cough, described by grade, between Day 0 and Day 28
- at least one solicited systemic AEFI between Day 0 and Day 28 (fever, headache, tiredness)
- at least one unsolicited AEFI between Day 0 and Day 28

AEFI should be reported at study visits during the first 28 days of the concerned subject.

SAE should be reported immediately but no later than 24 hours after detection. AEFI which lead to difficulties in breathing (asthma, spasmodic cough, pneumonia) will be considered as serious and reported to the DSMB and the sponsor.

- **Analysis strategy**

Analytical strategies will be the same as the primary endpoint analytical strategies.

2.1.3. OTHER SECONDARY ENDPOINT

1) Colonization of the BPZE1 strain in the nasopharyngeal mucosa:

Per dose, group and randomized allocation:

- Number and proportion of participants who have been colonized by the modified *B. pertussis* strain BPZE1 at each post-vaccination visit
- Number of visits during which bacteria are detected
- Magnitude of bacterial colonization (number of cfu) per post-vaccination visit
- Cough, spasmodic cough and any symptom from the respiratory tract will be described for colonized and not colonized participants

2) Immunogenicity:

Per dose, group, colonized/not colonized and randomized allocation:

- IgG and IgA antibodies against PT, FHA, PRN, and fimbriae 2/3 in serum at visits 2, 4, 6, 7, 8, 9 and 10
 - Geometric mean levels
 - Number and proportion of participants with positive responses, defined by at least 100% increase from pre- to post-vaccination, to at least 4 times MLD after vaccination

Samples will be tested blindly for *pertussis* specific antibodies in batch for each group. Antibody levels to PT, FHA, PRN, and fimbriae 2/3 will be expressed in IU/mL calibrated against reference antisera from the National Institute for Biological Standards and Controls.

- **Analysis strategy**

The immunogenicity criteria analysis will be performed on the mITT population and based on available data (without missing data handling) with the hypothesis of MCAR.

A robustness analysis will be performed and missing values will be imputed by the median of immunogenicity values in the placebo group.

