2.2.2. COMPARATIVE ANALYSIS

No statistical comparisons between arms or cohorts will be performed, as the trial is not designed for such comparisons. Intra-group comparisons will be performed for immunogenicity endpoints.

Intra-group comparisons for quantitative variables will be made using paired Student t-test or Wilcoxon paired signed-ranks test according to the distribution of variable of interest for analyzing change from baseline to post-vaccination within a given cohort arm. Transformations to normalize the variables can be made if necessary.

Intra-group comparisons for qualitative variables will be made using McNemar test or other, depending on the number of modalities of the variables of interest.

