2.3. CALCULATION CONVENTIONS FOR STATISTICAL ANALYSIS

2.3.1. CONVENTIONS FOR TIME CALCULATIONS

- Time between 2 dates in months = $\frac{(\text{Date 2} - \text{Date 1})}{30.4375}$
- Time between 2 dates in years = $\frac{(\text{Date 2} - \text{Date 1})}{365.25}$

2.3.2. CONVENTIONS FOR THE CALCULATION OF THE DIFFERENCE (DELTA) BETWEEN A MEASUREMENT AND THE ENROLMENT VISIT (D00)

The date of the enrolment visit (D00) is defined by the date of vaccination.

The difference to a D00 visit for a measurement taken at a visit posterior to D00 (follow-up visit DXX) will be calculated using the following formula:

- Delta = (measurement at DXX – measurement at D00)

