3.8. OTHER SECONDARY ENDPOINTS

1) Colonization of the BPZE1 strain in the nasopharyngeal mucosa:

Per dose, group and randomized allocation:

- Number and proportion of participants who have been colonized by the modified *B. pertussis* strain BPZE1 at each time point
- Number of days during which bacteria are detected
- Quantity of bacterial colonization (number of cfu) per post-vaccination visit
- Cough, spasmodic cough and any symptom from the respiratory tract will be described for colonized and not colonized participants

2) Immunogenicity:

Per dose, group, colonized/not colonized and randomized allocation:

- IgG and IgA antibodies against PT, FHA, PRN, and fimbriae 2/3 in serum at visits 2, 4, 6, 7, 8, 9 and 10
 - Geometric mean levels and 95%CI for pre and post vaccination (expressed in IU/mL calibrated against reference antisera from the National Institute for Biological Standards and Controls)

- Participants with positive responses (n, % and 95%CI), defined by at least 100% increase from pre- to post-vaccination, to at least 4 times MLD after vaccination (n, % at each post-vaccination time point)

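### The only planned robustness check for immunogenicity fills missing titres with the placebo median and ignores the participant's own baseline, so it can create false responders and false falls

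*Combined protocol and SAP*

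**What the plan says.** SAP 2.1.3 makes the main immunogenicity analysis an mITT analysis "based on available data (without missing data handling) with the hypothesis of MCAR". It then commits to one robustness analysis, in which "missing values will be imputed by the median of immunogenicity values in the placebo group". The rule makes no exception for the placebo arm. It does not say whether the median is taken per antigen, isotype and visit, whether it uses pooled placebo recipients, or whether missing baselines are also filled. SAP 2.3.4, on missing data, covers only dates and missing-value codes.

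The endpoints the rule feeds are these:

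- A positive response is "defined by at least 100% increase from pre- to post-vaccination, to at least 4 times MLD after vaccination" (SAP 2.1.3, repeated in 3.8).
- Change is the follow-up value minus the same participant's D00 value (SAP 2.3.2).
- "Intra-group comparisons for quantitative variables will be made using paired Student t-test or Wilcoxon paired signed-ranks test" (SAP 2.2.2).
- "Geometric mean levels and 95%CI for pre and post vaccination" (SAP 3.8).

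The first three compare a participant with their own baseline. The fourth does not.

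**The concern.** If a missing post-vaccination value is replaced by one constant M, the placebo median, that participant's change becomes M minus their own baseline. This is not an assumption of no vaccine effect for that person. Someone with a low baseline is given a rise and someone with a high baseline a fall, with nothing observed in either case. With 12 active participants per dose level, one misclassified person is visible in the response rate.

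A second problem arises where the placebo arm is filled with its own median. Values are added at the centre of the data and counted as observed, so the spread shrinks while the nominal sample size grows.

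At stake is whether the check can do its job. It is the one committed test of how far the MCAR analysis can be trusted, and for response and change it mixes a conservative shift with artefacts in both directions.

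**Working it through.** **Inputs from the documents.** There are 12 active and 4 placebo participants per group in Groups 1 to 3 (SAP 1.2.1). The 12 placebo recipients are pooled only if no clinically significant differences appear (SAP 3.4). PT and PRN IgG must be below 20 IU/ml at entry in Groups 1 to 3. Group 4 has 6 participants with PRN IgG of at least 20 IU/ml and no placebo (protocol V.2 and VI.2).

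**Assumptions, because the documents give none.** Log titres are normal and values are missing completely at random, with 1 to 3 of 12 missing. The between-person SD is 0.4 to 0.6 on the log10 scale or, as a wider range, 0.5 to 1.3 on the natural-log scale. The plan gives no figure for this rule, so there is none to reproduce.

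**Step 1, false responders and falls.** Take a participant with no true change, from a population whose median baseline equals M. The fill meets the 100% rise if baseline ≤ M/2, with probability Φ(−log 2 / SD):

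| SD | Probability |
|---|---|
| ln 0.5 | Φ(−0.693/0.5) = 8.3% |
| ln 0.9 | Φ(−0.693/0.9) = 22.1% |
| ln 1.3 | Φ(−0.693/1.3) = 29.7% |
| log10 0.4 | Φ(−0.301/0.4) = 22.6% |
| log10 0.5 | Φ(−0.301/0.5) = 27.4% |
| log10 0.6 | Φ(−0.301/0.6) = 30.8% |

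The range is therefore about 8% to 31% per imputed value. A counted response also needs M ≥ 4 times MLD. By symmetry an apparent halving or worse (baseline ≥ 2M) has the same probability.

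**Step 2, effect of one case.** 1/12 = 8.3 points. With one value missing and no responders, available data give 0/11 (exact 95% CI 0 to 28.5%). A false responder makes this 1/12 (0.2% to 38.5%). Counting the missing status as non-response gives 0/12 (0 to 26.5%).

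**Step 3, Group 4.** If Group 4 enters this analysis, an imputed PRN IgG value is a fall from the entry level whenever the placebo median stays below 20 IU/ml. The SAP defines mITT on randomized participants, so whether Group 4 is covered is unclear.

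**Step 4, placebo arm filled with its own median.** Simulation, n = 12, 100,000 runs:

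| Missing | GMT interval width, filled / available | Coverage |
|---|---|---|
| 1 | 0.90 | 92.7% |
| 2 | 0.81 | 89.8% |
| 3 | 0.71 | 85.6% |

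**Step 5, GMT intervals in active arms.** Let d be the distance in SDs between the arm's mean log titre and log M, k the number missing and m = 12 − k. The width ratio is t(11)·√(V/12) divided by t(m−1)·√(1/m), with V = [(m−1) + (mk/12)d²]/11. For k = 1, 2, 3:

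- d = 0: ratio 0.90, 0.80, 0.71; simulated coverage still 95.1%, 94.7%, 93.9%.
- The ratio passes 1 at d of about 1.6, 1.7, 1.9.
- d = 3: ratio 1.22, 1.31, 1.33.
- d = 2: simulated coverage 95.0%, 89.8%, 80.8%, with the mean shifted toward placebo by 0.17, 0.33, 0.50 SD. Simulated intervals here are slightly wider than with available data, so the loss of coverage is due to the shift.

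**Step 6, paired change.** With 1 or 2 missing, the simulated interval was 1.00 to 1.91 times as wide as with available data, because M minus own baseline brings in between-person variance.

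**Step 7, one strong-response case.** Take n = 12, 2 missing, a true 10-fold rise, log10 baseline SD 0.5 and change SD 0.2. The half-width for the post-vaccination GMT is 0.394 filled against 0.373 available; for change it is 0.293 against 0.139. The estimated rise is 10^(10/12) = 6.8-fold. Carrying own baseline forward gives the same 6.8-fold, and coverage of the GMT is 91% against 90% under the written rule.

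**The case against.** The strongest defence is that the rule is a deliberate no-effect assumption. Groups 1 to 3 are randomized within dose group, so the placebo level is a legitimate no-effect reference for the geometric mean, the first-listed immunogenicity measure. The pull toward placebo is then the intended conservatism, and Step 7 shows that an own-baseline fill produces the same attenuation. This stands for the geometric mean. It does not rescue response and change, where the reference has to be the participant's own baseline.

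A reader might infer that the rule makes confidence intervals too narrow throughout. Steps 5 to 7 do not support that. Narrowing with loss of coverage is clear for the placebo arm's own GMT. Arms close to placebo have narrower intervals but nearly nominal coverage, strongly responding arms have wider ones, and paired-change intervals are about equal or wider.

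The Step 1 probabilities also need care. They rest on assumed SDs, set the 4 times MLD condition aside and use an untruncated lognormal, although entry limits truncate PT and PRN IgG in Groups 1 to 3. It would also go too far to say that the plan imputes missing baselines: the text is silent, and the request there is for clarification.

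Finally, the likely impact is small. The main analysis does not impute, no between-arm comparisons are planned, and information from only 1 of 385 planned visits (0.26%) was missing in the earlier trial (protocol III.2). That stands, except that missingness at the SAP's added 12-month visit is unknown.

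**Conclusion.** The concern holds for the endpoints that use own baseline, and for the placebo arm's own geometric mean. Followed as written, the rule can turn a non-responder into a responder or show a fall that did not occur. Each has a probability of about 8% to 31% per imputed value under the assumed SDs, and a counted response also needs the placebo median to reach 4 times MLD. One such case is worth 8.3 points in a 12-person arm. Self-filling the placebo arm lowers GMT interval coverage to about 93%, 90% or 86% with 1, 2 or 3 of 12 missing.

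A reader might conclude that the check can neither support nor refute the main result. For the mean that is not so: attenuation toward no effect is a usable conservative case. The point is minor, since it concerns a robustness analysis of a secondary endpoint and little may be missing.

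**What to change.** Reword the robustness rule in SAP 2.1.3 as follows:

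- Set a missing post-vaccination titre to the participant's own D00 value on the log scale. The fold change is then exactly 1, so the fill creates neither a responder nor a fall.
- Count missing response status as non-response.
- Do not impute a missing D00 value.
- Do not fill the placebo arm with its own median.

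State whether Group 4 is included, and report the number of filled values by arm and visit.

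This is still single imputation. A carried-forward value adds a zero change, which can itself shorten paired-change intervals in an arm with little true change, so the result should be read as a no-response scenario. Multiple imputation from placebo fold changes, or a mixed model on log titre, would handle the uncertainty better but is optional at this sample size. Longitudinal models are already allowed as ancillary analyses (protocol XV.2.1, SAP 3.9).

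The cost is a short change to SAP wording and minor programming. No extra data or visits are needed, and the main analysis is unchanged.

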2.1.4. EXPLORATORY ENDPOINT

- IgA antibodies against PT, FHA, PRN, and fimbriae 2/3 in nasopharyngeal aspirate at visits 2, 4, 6, 7, 8, 9 and 10
 - Geometric mean levels
 - Number and proportion of participants with positive responses, defined by at least 100% increase from pre- to post-vaccination, to at least 4 times MLD after vaccination
- Median levels of cytokines in nasopharyngeal aspirate
- Median levels of cytokines in cell culture supernatants after stimulation of PBMC with PT, FHA, PRN and unrelated antigen
- Median number of spot-forming units determined by ELISpot/FluoroSpot assay of pertussis-specific cytokine-positive T-cells after stimulation of PBMC with PT, FHA, PRN and unrelated antigens.
- Median number of spot-forming units determined by ELISpot assay of pertussis-specific IgG-producing memory B-cells after stimulation of PBMC with PT, FHA, PRN and unrelated antigens.

2.1.5. INTERIM REPORTING TO DSMB

Interim safety reports using descriptive statistical methods for the DSMB will be performed when all volunteers of a given group will have reached day 28, before opening enrolment to the next cohort (next higher dose).

2.1.6. CONFIDENTIAL INTERIM ANALYSIS FOR DECISION MAKING FOR PHASE II DESIGN

An analysis of the safety data and BPZE1 nasopharyngeal colonization data will be performed when culture results are available from twenty-eight days after vaccination of the last volunteer in the high dose group 3 and include analyses of the safety endpoints and the colonization endpoints up to D28 in groups 1, 2 and 3. The analysis report will provide summary data only (i.e. no information about individual volunteers) for ILiAD to present to regulatory agencies and expert consultants to aid in designing a Phase II study and its financial requirements. Since the long-term follow-up in the trial will still be ongoing at that time, this analysis will be performed by a statistician not involved in the rest of the trial procedures and analysis (i.e. a statistician designated by ILiAD outside of the EUCLID platform). The Interim Analysis statistician will provide the summary data to the VP of Development as a representative of ILiAD, who will only share this data on a need to know basis with regulatory agencies, as well as employees, consultants, or prospective partners of ILiAD who have signed a confidentiality agreement. In order not to bias the conduct of the long-term follow-up and other trial procedures of the ongoing trial, the Interim Analysis data will not be shared with any individuals directly involved with executing the Phase Ib study until after data lock.

2.2. STATISTICAL METHODS

2.2.1. DESCRIPTIVE ANALYSIS

The frequency and proportion of available data are described for each variable.

Quantitative variables will be described in terms of absolute frequency, mean, standard deviation, confidence interval of the mean, median, interquartile range, minimum, and maximum. Geometric means and their confidence interval will be performed for titers.

Qualitative variables will be described in terms of number, proportion and exact binomial confidence interval of proportion.

Descriptive analysis is performed overall and by intervention group.

2.2.2. COMPARATIVE ANALYSIS

No statistical comparisons between arms or cohorts will be performed, as the trial is not designed for such comparisons. Intra-group comparisons will be performed for immunogenicity endpoints.

Intra-group comparisons for quantitative variables will be made using paired Student t-test or Wilcoxon paired signed-ranks test according to the distribution of variable of interest for analyzing change from baseline to post-vaccination within a given cohort arm. Transformations to normalize the variables can be made if necessary.

Intra-group comparisons for qualitative variables will be made using McNemar test or other, depending on the number of modalities of the variables of interest.

2.3. CALCULATION CONVENTIONS FOR STATISTICAL ANALYSIS

2.3.1. CONVENTIONS FOR TIME CALCULATIONS

- Time between 2 dates in months = $\frac{(\text{Date 2} - \text{Date 1})}{30.4375}$
- Time between 2 dates in years = $\frac{(\text{Date 2} - \text{Date 1})}{365.25}$

2.3.2. CONVENTIONS FOR THE CALCULATION OF THE DIFFERENCE (DELTA) BETWEEN A MEASUREMENT AND THE ENROLMENT VISIT (D00)

The date of the enrolment visit (D00) is defined by the date of vaccination.

The difference to a D00 visit for a measurement taken at a visit posterior to D00 (follow-up visit DXX) will be calculated using the following formula:

- Delta = (measurement at DXX – measurement at D00)

2.3.3. CONVENTIONS FOR BMI CALCULATIONS

- European BMI = $\frac{\text{Weight}(kg)}{\text{Height}^2(m)}$
- US BMI = $\frac{\text{Weight}(Pounds) \times 703}{\text{Height}^2(inches)}$

2.3.4. MISSING DATA

- Conventions for dates

Except in special cases, if the day is missing, the convention is to use the value “15”, i.e. mid-month. If the day and month are missing, the convention is to use the value “1” for days and the value “7” for month, i.e.

mid-year. This convention allows us to measure time estimates. The statistician makes these imputations at the time of analysis and consistency is checked at the time of data review.

- Conventions for handling missing data

The following values are used in the database to describe the missing data:

- « NK » or « K »: Unknown
- « ND » or « D »: Not done
- « NA » or « A »: Not applicable

There is no distinction in the statistical analyses according to the type of missing data.

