1.2.2. TRIAL TIMELINE

Site opening	: August 2015
First Visit First Subject (group 1)	: September 2015
First randomization (group 1)	: September 2015
First Visit First Subject (group 2)	: October 2015
First randomization (group 2)	: November 2015
First Visit First Subject (group 3)	: January 2016
First randomization (group 3)	: January 2016
First Visit First Subject (group 4)	: March 2016
First vaccination (group 4)	: March 2016
First Visit Last Subject	: February 2016
Last Visit Last Subject	: February 2017
Antibody assays	: August 2015 – April 2017
Exploratory laboratory assays	: April 2016 – December 2017
Final statistical analysis	: October 2016 – June 2017
Clinical study report	: February 2017 and then August 2017

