2.1.1. PRIMARY SAFETY ENDPOINT

- **Definition**

The primary safety endpoint will be the number and proportion of participants, per dose group and randomized allocation, with at least one of the following adverse events between Day 0 (Visit 2) and Day 28 (Visit 8):

- Cough and spasmodic cough of grade 2 or higher.
- Other respiratory tract AE related or possibly related to vaccination of grade 3 or higher.
- Any other AE related or possibly related to vaccination of grade 3 or higher.

- **Strategy for the main analysis**

The main analysis is conducted:

- By modified intention to treat: This means that all randomized participants who received a vaccine dose are included in the analysis in the group to which they were initially randomized and all their data is used regardless of protocol deviations during the trial/study.
- In this analysis, participants with missing follow-up data will be assumed to be event-free, unless the site has any knowledge of a safety event having occurred and has notified this in the e-CRF.

- **Strategy for secondary analyses**

- With the strategy of *definitely missing follow-up data (i.e. premature termination of follow-up) = failure*.
(For non-compliant participant, it will be assumed that no safety event occurred during the missing visits)

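### The SAP's date convention has no adverse-event rule and no bound, so it can place a partially dated event outside the Day 0–28 safety window (minor)

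*Combined protocol and SAP*

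**What the plan says.** **The convention.** SAP 2.3.4 (Missing data) says: "Except in special cases, if the day is missing, the convention is to use the value" 15, described as mid-month. It continues: "If the day and month are missing, the convention is to use the value" 1 for the day and 7 for the month, that is, 1 July. The stated purpose is to allow time estimates. The statistician imputes at the time of analysis, and "consistency is checked at the time of data review". The special cases are not defined. No separate rule is given for adverse-event onset, and nothing ties an imputed date to the vaccination date, the reporting visit or Day 28.

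**The windows.** SAP 2.1.1 defines the primary safety endpoint as participants with at least one qualifying event from Day 0 (Visit 2) to Day 28 (Visit 8). SAP 2.3.2 fixes the origin: "The date of the enrolment visit (D00) is defined by the date of vaccination". Each endpoint listed in SAP 2.1.2 uses a Day 0–28 or Day 4–28 window. The DSMB reports in SAP 3.10 also split results into pre- and post-vaccination periods.

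**The nearest related rule.** In the main analysis (SAP 2.1.1), "participants with missing follow-up data will be assumed to be event-free, unless the site has any knowledge of a safety event having occurred". That covers absent follow-up. It does not cover an event that was reported with an incomplete date.

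**The concern.** A mid-month or mid-year value is a reasonable neutral guess for a long duration. It suits a 29-day window poorly, because the imputation error can be as long as half a month or half a year. An event dated only to the month of vaccination goes before vaccination whenever the participant was vaccinated after the 15th. An event dated only to the following month can go past Day 28.

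Whether a true in-window event survives then depends on the calendar day of vaccination, which has no clinical meaning. For a safety endpoint, losing such an event is the non-conservative error. The arms are small, so one event matters, and the same counts go to the DSMB before each dose escalation.

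**Working it through.** **1. The plan's own figures.** SAP 1.3 gives 80% probability of at least one event among 12 at a true rate of 12.6%, and upper 95% bounds of 26% for 0/12 and 10% for 0/36.
- 1 − (1 − 0.126)^12 = 0.801, which agrees.
- The exact (Clopper–Pearson) two-sided upper bound for zero events is 1 − 0.025^(1/n). This gives 26.5% for n = 12 and 9.7% for n = 36, which agree to rounding.

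The documents give no figure for the effect of the date rule, so it was enumerated.

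**2. Inputs.**
- Window: Days 0 to 28 from vaccination, 29 possible onset days (SAP 2.1.1, 2.3.2).
- Calendar: first randomization or vaccination in September 2015, November 2015, January 2016 and March 2016 for groups 1 to 4 (SAP 1.2.2). Exact days are not given.
- Assumption: vaccination uniform over 1 September 2015 to 31 March 2016 (213 dates) and onset uniform over Days 0–28, giving 213 × 29 = 6,177 combinations.

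**3. Only the day missing.** Replace the onset by the 15th of its month, set d = imputed date − vaccination date, and classify as before (d < 0), in (0 ≤ d ≤ 28) or after (d > 28).

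| Result | Combinations | Share |
|---|---|---|
| Before vaccination | 889 | 14.4% |
| Day 0–28 | 4,553 | 73.7% |
| After Day 28 | 735 | 11.9% |

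Misplaced: (889 + 735) / 6,177 = 26.3%.

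Using only the start month of each group, groups 1 and 2 lose 13.8% + 12.1% = 25.9%, and groups 3 and 4 lose 15.1% + 11.7% = 26.8%.

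**4. Spread by vaccination day.** Vaccination on the 1st of any of these months loses 0 of 29 onset days. Vaccination on the 16th loses 29 of 29, except in February 2016, when it loses 14 of 29. Worked example, vaccination on 16 September 2015: onsets on 16–30 September (15 days) become 15 September, Day −1; onsets on 1–14 October (14 days) become 15 October, Day 29. All 29 fall outside.

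**5. Day and month missing.** 1 July lies within Days 0–28 only for vaccination from 3 June to 1 July. For the scheduled start months it falls as follows.

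| Group | Start month | Position of 1 July of the same year |
|---|---|---|
| 1 | September 2015 | 62–91 days before vaccination |
| 2 | November 2015 | 123–152 days before vaccination |
| 3 | January 2016 | Day 152–182 |
| 4 | March 2016 | Day 92–122 |

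None of the 6,177 combinations stays in the window.

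**6. The opposite error.** Applying the day-missing rule to true onsets on Days 29–59 pulls about 11% to 15% into the window, depending on the month of vaccination.

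**7. One lost event.** If a participant's only qualifying event is moved out:
- one active arm: 1/12 = 8.3% (exact 95% CI 0.2% to 38.5%) becomes 0/12 (upper bound 26.5%);
- pooled active arms: 1/36 (upper bound 14.5%) becomes 0/36 (upper bound 9.7%).

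**The case against.** The strongest reply is that this will hardly ever happen.
- Protocol XIII.2 has cough, spasmodic cough and solicited events documented daily in a diary from Day 0 to Day 28. Protocol VI.3.4 to VI.3.9 has the diary reviewed, and events since the previous visit asked about, at six visits by Day 28. An event with an unclear day is normally still bracketed between two visits.
- Protocol XVI.3 requires requested CRF items to be completed and sends inconsistencies to the investigator as queries. XVI.4 requires a data review meeting before lock.
- The convention has an exception clause and a consistency check, and it is meant for time estimates. The SAP does not say that window membership is decided from imputed dates.
- DSMB reports append listings of individual events (SAP 3.10), the analysis makes no between-arm tests (SAP 2.2.2), and the rule treats vaccine and placebo alike.

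Most of this stands, and it is why the point is minor. Exposure lies mainly with unsolicited events, which are entered spontaneously and feed the grade 3 or higher components. The consistency check would probably catch an onset dated before vaccination, the larger share of the misplacement. It is less sure to catch one moved past Day 28: events are collected to Visit 9 (Protocol VI.3.11), so a late date looks plausible unless compared with the reporting visit. Neither the exception nor the check is specified for adverse-event onset, and no other rule says how to place a partially dated event.

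A reader might infer that the rule routinely strips events from the primary endpoint. The documents do not support that. Nearly three quarters of day-missing onsets stay in, some later events are added, and the percentages apply only to events with partial dates, whose frequency is not given.

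**Conclusion.** The gap is real and minor. As written, the convention can misplace a partially dated adverse event relative to vaccination and Day 28, in either direction. For in-window onsets with only the day missing, the average misplacement is about 26%, ranging from 0% to 100% by calendar day of vaccination. With the month also missing, misplacement is certain for every scheduled group.

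The average rests on uniform vaccination dates and onset days. Each dose group is vaccinated over five vaccination days (SAP 1.2.1), so the share in any one group could lie well away from 26%. All these figures also assume that the imputed date decides window membership, which the SAP neither states nor excludes. The expected effect on the reported rate cannot be calculated, because the number of partial dates is unknown; it is probably small. The case for acting is that one event changes the reading of an arm of 12, and the correction costs almost nothing.

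**What to change.** Add an adverse-event rule to SAP 2.3.4:
- For a partial onset date, impute the earliest date that agrees with the known date parts, is on or after vaccination, and lies within the diary or visit interval in which the event was reported.
- Count the event in Day 0–28 unless the known date parts, the stop date or the reporting visit show otherwise.
- Keep the mid-month and mid-year convention for other durations.

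Under this rule no true in-window onset is lost through imputation: the imputed date is never before Day 0 and never later than the true onset, provided the recorded date parts and interval are right. For the Day 4–28 cough endpoint, the earliest date could fall before Day 4, so the sentence should count the event there too if any compatible date lies in that window.

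The cost is a sentence or two of SAP text, with no change to data collection or conduct. A few events that began outside the window may be counted, for example when the interval before Visit 8 runs past Day 28, so the reported rate may be slightly less favourable. Listing events with imputed onset would let a reader see how many there are.
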